## **4.4 Clinical Experience**

In humans, the over ingestion of sodium chlorate (a similar compound to chlorine dioxide) based herbicides revealed a minimal lethal dose of 220 mg/kg of sodium chlorate in adult humans according to one study (16). Another study in humans showed that chlorine dioxide and its metabolites (chlorite and chlorate) are well tolerated at doses of 2.5 mg or less (<0.04 mg/kg assuming 70 kg average man)

when ingested daily for 12 weeks, except potentially in patients with glucose-6-phosphate dehydrogenase (G6PD) deficiency (17). A prospective epidemiological study in humans exposed to chlorine dioxide (0.25 – 1.1 mg/L) after ingesting drinking water for 12 consecutive weeks showed no adverse effects when compared to a control group ingesting water without chlorine dioxide (18).

There are no data we are aware of evaluating the safety and efficacy of ClōSYS® Unflavored Oral Rinse for the prevention, delay, or reduction in RT related OM in patients being treated for HNC. As mentioned above, a meta-analysis of other similar orally available, topically delivered antimicrobials and anti-inflammatory agents have shown equipoise for mitigating RT induced OM (5). ClōSYS® Unflavored Oral Rinse is an FDA approved, commercially available product which is approved for 15 ml twice daily (30 second) rinse applications (19)(20). Two clinical trials of 15 patients each have demonstrated that chlorine dioxide rinsing is safe and effective in the treatment of halitosis and reduction of plaque build-up, while none reporting toxicities associated with the rinse (4)(21).

## **5. INVESTIGATIONAL PRODUCT, INTERVENTION, DEVICE**

### **5.1 Investigational Product, Intervention or Device**

ClōSYS® Unflavored Oral Rinse containing 0.1% (w/v) stabilized chlorine dioxide used twice daily with 15 mL per rinse for 30 seconds

### **5.2 Investigational product, intervention or device supply**

The IP (ClōSYS® Unflavored Oral Rinse) is a commercially available, over-the-counter, product which is currently FDA approved for the treatment of halitosis and general oral hygiene care. The following products will be supplied by Rowpar Pharmaceuticals Inc. specifically for the purpose of this study in 16 oz. white, opaque bottles, along with measuring cups, requiring no additional preparation. ClōSYS® Unflavored Oral Rinse or Placebo Oral Rinse will be labelled in such a way that they are not identifiable by subjects or investigators.

- a.** ClōSYS® Unflavored Oral Rinse (also referred as ClōSYS® Unflavored Alcohol-Free Oral Rinse).
- b.** Unflavored Placebo Oral Rinse. The study placebo will be identical in appearance to the IP and without stabilized chlorine dioxide.

### **5.3 Investigational product, Intervention or Device Accountability**

Because the IP (ClōSYS® Unflavored Oral Rinse) and Placebo Oral Rinse will be supplied directly to the Banner UMC Research (BUMC-N) pharmacy for use in this study, the receipt of shipment, dispensing and return or destruction records will be tracked using the Investigational Agent Accountability Record or other applicable and similar record. Once a signed order for IP is received by pharmacy, the IP will be given to the research staff to dispense to the study participant. Participants will be asked to keep a rinse diary, which will include date, time, and length of rinsing. All containers will be returned by the patient

and then taken to pharmacy by the research staff. The amount of rinse solution taken will be documented by taking the initial volume of rinse given to the patient and subtracting any oral rinse not used by measuring the returned residual volume of solution. The unused remaining rinse solution will then be destroyed in accordance with the BUMC Pharmacy policy. We plan to distribute and collect rinse solution bottles at weekly intervals.

#### **5.4 Storage**

IP (ClōSYS® Unflavored Oral Rinse) and placebo will be stored at room temperature per manufacturer recommendations in the BUMC-N pharmacy with limited access to personnel.

#### **5.5 Preparation**

Once an order is written by the treating doctor and received by pharmacy, the pharmacist or technician will dispense the randomized, blinded study drug. A member of the research staff will pick up the prescription bottle and will give the bottle directly to the subject.

#### **5.6 Handling**

There is no special handling required for the IP.

### **6. SUBJECT ELIGIBILITY**

Investigators will maintain an electronic subject log (in the UACC OnCore system and/or Redcap) of all potential (i.e. consented) study subjects, which will include as applicable (demographics, informed consent, eligibility, treatment assignment, on treatment, off treatment, follow up and off study dates).

#### **6.1 Inclusion Criteria**

- a. Able to provide properly obtained written informed consent
- b. Age 18 years or older
- c. Pathologically-confirmed diagnosis of head and neck malignancy (stage I-IV)
- d. Planned to receive high dose RT  $\geq 50$  Gy to visualizable oral cavity and/or oropharyngeal mucosa, with or without administration of concurrent systemic therapy.
- e. Karnofsky Performance Status of  $\geq 60$ , within 90 days of registration
- f. Baseline hematocrit  $> 20$  within 90 days of registration to the study
- g. Willingness to complete OMWQ and PRO-CTCAE forms at each designated time point along with oral rinse diary
- h. Life expectancy  $\geq 3$  months
- i. Willing to tolerate oral rinsing for 30 second intervals
- j. Negative serum pregnancy test in females of childbearing age
- k. Must be willing to use an effective form of birth control if female and of childbearing potential

## 6.2 Exclusion Criteria

- a) Known hypersensitivity to chlorine dioxide products
- b) Chlorine dioxide product usage within the past 7 days prior to registration for this study
- c) Utilization of any antibiotic medications (orally topical or systemic) within past 7 days prior to registration for this study
- d) Utilization of supraphysiological corticosteroid medication (>10 mg oral prednisone or equivalent dose) for chronic indication
- e) Sjogrens disease
- f) Medically documented glucose-6-phosphate dehydrogenase (G6PD) deficiency
- g) Planned daily RT of less than 5 weeks duration
- h) Known history of HIV or AIDS
- i) Current pregnancy

## 6.3 Enrollment

The source of subjects is the patient population at the Banner University Medical Group/University of Arizona Cancer Center. Patients who are scheduled as part of their routine care to consult with the radiation oncologist for definitive treatment of HNC (stage I-IV) will be provided with information regarding this study.

Before subjects may be entered into the study, a copy of the written institutional review board (IRB) approval of the protocol, informed consent form (ICF), and all other applicable subject information and/or recruitment material will be on file at the University of Arizona. All efforts will be made to consent the subject at an already scheduled appointment with the radiation oncologist. It is possible they would need to come in for an additional appointment. This could be either at their initial consult visit or during their CT simulation appointment. Subjects will have the opportunity to take their time in making a decision to join the study and will be encouraged to take the Informed Consent Form home and discuss it with whomever they would like. The treating physician will explain to the subjects the risks and benefits. They will be informed that their participation is voluntary, and lack of participation will not affect the subject's relationship with the treating staff or our facility. Subjects will be consented by either the PI, or the Research Staff of the Radiation Oncology department. The written informed consent document will be signed and personally dated by the subject and completed to a fully executed informed consent document and processed per the University of Arizona standard operating procedures.

Subjects will also be made aware that should they consent, they can withdraw their consent at any time. When new information becomes available, it will be given to the patient as soon as possible, either at their next visit, or if that is more than 30 days away, by phone call. Once an approved revised consent form is submitted and approved by the IRB, the subject will be asked to sign the new consent and the subject will be notified of the change to the consent form. The AZCC Verification of Consent form will be completed at the time the subject is consented. This form includes information pertaining to who is present at

consenting, that the consent form was reviewed with the subject, the subject understood the consent form, and the date and the time of the consent. Also documented will be the version of the Subject Consent form and the HIPAA form.

Subjects will be registered by the University of Arizona Research Pharmacy. Once subjects complete the screening process for this study and are deemed eligible, required information will be given to the pharmacy staff to register the subject in a stratification/randomization system designed by biostatistician [name]. Each subject will be identified by a unique sequential subject identification number. This number will be used to identify the subject throughout the clinical study and will be used on all applicable study documentation related to that subject. The subject identification number will remain constant throughout the study. The sponsor will be providing study IP with blinded labeling and only they will know which label corresponds with active agent or placebo.

## **7. STUDY PLAN**

### **7.1 IP/treatment/intervention/device regimen**

Subjects will be stratified by whether or not they will be receiving concurrent systemic therapy and then randomly assigned to receive either ClōSYS® Unflavored Oral Rinse twice daily or placebo oral rinse twice daily from the start of RT to their 1-month RT follow-up appointment. Assignment of IP will be done in a double-blinded fashion. Both active rinse and placebo rinse will be formulated to look identical in appearance.

Subjects will receive verbal and written oral hygiene instructions and 11 bottles of either (16 oz. each) of ClōSYS® Unflavored Oral Rinse or placebo oral rinse. Subjects will also receive measuring cups for dispensing the rinse (15 ml per dose) and a diary for recording usage in order to track their rinsing adherence, as well as notating any subjective effects possibly attributable to the rinse.

Treatment with IP will start on the morning of day 1 of RT and subjects will be advised to use the IP (preferably after meals) at approximately 8 a.m.  $\pm$  3 hours and 8 p.m.  $\pm$  3 hours, with 15 mL per rinse for 30 seconds during each session. They will be instructed to take nothing by mouth for 20 minutes following their rinse to allow it to take effect. They will note in their patient's log the date, time, and duration of rinsing. Subjects will be instructed to continue with other standard oral hygiene practices we offer to our RT patients, including alkaline saline rinses, honey, miracle mouthwash, etc.

Baseline tobacco history including type of tobacco, number of pack-years, duration of smoking, and quit date if applicable will be recorded. This will be captured using the Tobacco Assessment Questionnaire (see section 27). Baseline dental evaluation counting number of teeth and generally graded condition (excellent, good, fair, poor) will be recorded. Baseline weight, BMI, and history of recent (3 months) weight loss will be recorded. Nutritional intake status (solids and liquids, liquids only, no oral intake) and utilization of enteral versus

parenteral feeding will be noted. HPV status of malignancy will be recorded. One week up until registration, concomitant medications will be collected.

Subjects will be seen once per week per standard of care for on-treatment visits (OTVs). Radiation treatments may be 6 or 7 weeks at the discretion of the treating physician. Vital signs and weight measurement along with grading of common head and neck side effects per common terminology criteria for adverse events (CTCAE v5.0) will be performed. CTCAE items will include generalized weakness, skin reaction, weight loss, dry mouth, sore throat, dysphagia, anorexia, dysgeusia, voice alteration, and neck edema. Physical examination will include focused evaluation of the head and neck region, with particular attention paid to documenting skin reaction and oral mucositis (OM).

At baseline (for example during CT-simulation), during weekly OTVs, and at their 1-month post-RT follow-up appointment, physician grading of OM will occur via intraoral examination utilizing the World Health Organization (WHO) Scale, as described in the table below:

Grade	Description
0 (none)	None
I (mild)	Oral soreness, erythema
II (moderate)	Oral erythema, ulcers, solid diet tolerated
III (severe)	Oral ulcers, liquid diet only
IV (life-threatening)	Oral alimentation impossible

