## 1.4 Patient Population

Eligible subjects must be able to understand and sign the study specific subject consent form. They must be  $\geq$ 18 years of age, have a Karnofsky Performance Status Scale (KPS) of  $\geq$ 60 with confirmed histologic or cytologic diagnosis of HNC (stage I-IV) for which they are receiving definitive or post-operative treatment with either RT alone or in combination with systemic therapy. Subjects may not have previous allergies to chlorine dioxide products and must fulfill the inclusion and exclusion criteria found in Section 6. Approximately 24 subjects will be randomized in a 1:1 ratio to stabilized chlorine dioxide rinse and placebo rinse. Twenty evaluable subjects (10 in each group) are needed in this pilot study to meet 81% statistical power (assuming a one-sided alpha of 0.05). We plan to recruit an additional 4 subjects to account for a 20% drop out/study non-compliance rate to ensure we have 20 evaluable subjects.

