**References:**

WHO: <http://www.who.int/en/>

At baseline (for example during CT-simulation), during weekly OTVs, and at their 1-month post-RT follow-up appointment, intraoral photo-documentation will be taken and uploaded into patient specific Cerner electronic medical record charts utilizing the Cerner Camera Capture application via handheld mobile devices. These will be filed with study identifier only and not the subject name.

Patient reported assessment of OM will be evaluated at baseline (for example during CT-simulation), at OTVs during weeks 2, 4, and 6 of RT, and at their 1-month post-RT follow-up appointment, with the OMWQ (6) and PRO-CTCAE. The OMWQ questionnaire contains 9 items with the total ranging from 0 to 54.

Whole Unstimulated Saliva (WUS) will be collected at baseline (prior to first treatment), at OTVs during weeks 2, 4, and 6 of RT, and at the 1-month post-RT follow-up appointment. Further information on WUS collection and analyses is provided in Appendix A.

Microbiome samples will also be collected at baseline (prior to first treatment), at OTVs during weeks 2, 4, and 6 of RT, and at the 1-month post-RT follow-up appointment, immediately following collection of patient WUS. Further information on microbiome collection and analyses is provided in Appendix B.

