### **9. STUDY PROCEDURES**

#### **9.1 Screening and Baseline**

Potential subjects will enter the screening period of the study after a completely executed informed consent has been obtained. See Section 26 (Study Schedule) for full list of baseline evaluations.

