#### **11.5 Description of adverse events and reporting procedures:**

##### **ADVERSE EVENTS**

An adverse event (AE) is any untoward medical occurrence in a patient or clinical investigation subject administered a pharmaceutical product and that does not necessarily have a causal relationship with this treatment. An AE can therefore be any unfavorable and unintended sign, symptom, or disease temporally associated with the use of a medicinal (investigational) product, whether or not related to the medicinal (investigational) product.

Adverse events will be recorded on the UACC adverse events record form and reviewed by the Principal Investigator. For this study we will focus on collecting the AEs that may be related to the investigational product and/or radiation therapy/chemotherapy with specific focus on generalized weakness, skin reaction, weight loss, dry mouth, sore throat, dysphagia, anorexia, dysgeusia, voice alteration, and neck edema.

All adverse events will be classified using NCI Common Terminology Criteria for Adverse Events (CTCAE) version 5.0 and will address:

- Grade

- Relationship to study drug (not related, unlikely, possible, probable, definitely)
- Relationship to radiation and/or chemotherapy (not related, unlikely, possible, probable, definitely)
- Causality other than study drug (disease related, concomitant medication related, intercurrent illness, other)
- Date of onset, date of resolution
- Frequency of event (single, intermittent, continuous)
- Event outcome (resolved, ongoing, death)
- Action taken (none, held, dose reduced, discontinued, medication given)

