## 26. STUDY SCHEDULE

Test or Procedure	Baseline (Prior to first treatment)	Week 1 (±1 day)	Week 2 (±1 day)	Week 3 (±1 day)	Week 4 (±1 day)	Week 5 (±1 day)	Week 6 (±1 day)	Week 7 (if applicable) (±1 day)	1-month post-RT follow-up visit (+21 days)	
Informed consent	X									
Medical history, BMI and tobacco history 1	X									
Concurrent meds 2	X		X		X		X		X	
Physical Exam including dental eval and photos 3	X	X	X	X	X	X	X	X	X	
Hct 4	X								X	
Malignancy info 5	X									
Registration & Randomization	X									
OMWQ and PRO CTCAE 6	X		X		X		X		X	
WUS and Microbiome Collection 7	X		X		X		X		X	
Dispense IP/placebo	X	X	X	X	X	X	X	X		
Adverse Event Check 8		X	X	X	X	X	X	X	X	
Rinse Diary and Observational Form 9	X	X	X	X	X	X	X	X	X	

Test or Procedure	Baseline (Prior to first treatment)	Week 1 (±1 day)	Week 2 (±1 day)	Week 3 (±1 day)	Week 4 (±1 day)	Week 5 (±1 day)	Week 6 (±1 day)	Week 7 (if applicable) (±1 day)	1-month post-RT follow-up visit (+21 days)	
Collect Unused IP/placebo 10		X	X	X	X	X	X	X	X	
Documentation of RT treatment interruptions									X	

1= Complete medical history will include demographics and will be performed within 90 days of registration. Tobacco history will be collected using the Tobacco Assessment Questionnaire.

2= Review medications including usage of any chlorine dioxide, antimicrobials, or corticosteroids within last 7 days prior to registration. Additionally, will review usage of honey, baking soda and salt rinses, magic mouthwash, viscous lidocaine, doxepin solution, chlorhexidine, and other antimicrobials, corticosteroids, anti-inflammatories, etc during study period. Only medications related to either cancer therapy or treatment of a related adverse events will be collected. No other concomitant medications will be tracked.

3= All PEs to include vitals (BP, pulse, temperature, weight), KPS scoring, and OM grading per WHO scoring criteria (see section 7.1)

4= Hematocrit within 90 days of study registration

5= Confirmation of cytologic or histologic evidence of HNC and documentation of stage

6= Oral Mucositis Weekly Questionnaire and Patient Reported Outcomes Common Terminology Criteria for Adverse Events

7= Whole Unstimulated Salivary and Microbiome Collection (see section 7.1)

8= Common Terminology Criteria for Adverse Events (CTCAE) v.5 will be used for grading of generalized weakness, skin reaction, weight loss, dry mouth, sore throat, dysphagia, anorexia, dysgeusia, voice alteration, and neck edema

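### No clinician CTCAE grade of the ten tracked toxicities is planned before the first rinse, so change from a pre-exposure grade cannot be computed

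*Combined protocol and SAP*

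**What the plan says.** Section 7.1 describes the weekly on-treatment visits and says that at them "grading of common head and neck side effects per common terminology criteria for adverse events (CTCAE v5.0) will be performed". It does not name baseline for this grading. Later in the same section, WHO mucositis grading, photographs, patient questionnaires, saliva and microbiome samples are each given a baseline time point; for the questionnaires the text reads "Patient reported assessment of OM will be evaluated at baseline (for example during CT-simulation".

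In Section 26, the row "Adverse Event Check 8" (the 8 is a footnote mark) is empty in the baseline column and marked at weeks 1 to 7 and at the 1-month visit. Footnote 8 says that CTCAE version 5 "will be used for grading of generalized weakness, skin reaction, weight loss, dry mouth, sore throat, dysphagia, anorexia, dysgeusia, voice alteration, and neck edema".

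Section 9.1 tells the reader: "See Section 26 (Study Schedule) for full list of baseline evaluations". Section 7.1 adds: "Treatment with IP will start on the morning of day 1 of RT".

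Section 11.5 makes the same ten items the focus of adverse event collection. For each event it asks for a grade, onset and resolution dates, and attribution, including "Relationship to study drug (not related, unlikely, possible, probable, definitely" and matching scales for radiation or chemotherapy and for other causes. Section 17.1 defers the safety analysis to the end of the study. It does not say whether an event must be new or worsened to be counted.

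**The concern.** The trial enrols patients with stage I to IV disease who are receiving "definitive or post-operative treatment with either RT alone or in combination with systemic therapy". Such patients can plausibly start RT with difficulty swallowing, a changed voice, neck swelling, a sore throat or weight loss from the tumour or from surgery. If the first CTCAE grade is taken after both rinse and RT have begun, the safety tables have no starting value on that scale. A stable symptom and one that has worsened may then carry the same grade.

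This matters because Section 4.4 knows of no safety data for this rinse in this setting, and Section 4.2 hopes the results will support a phase III trial. With about 12 patients randomized per arm, a few patients who enter with a symptom can shift an arm's toxicity rate visibly.

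**Working it through.** The plan states no figure on this point, so the check is a reading of the schedule, an item-by-item count and one illustration.

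**Step 1. Is there any planned pre-exposure grade?** Section 7.1 ties the grading to on-treatment visits, which cannot come before the first day of RT, and rinsing starts that morning. The Section 26 row is blank at baseline. Footnote 3 to Section 26 lists what every physical examination includes: vitals, KPS and the WHO mucositis grade, with no CTCAE grade. The baseline paragraph in Section 7.1 names some details that Section 26 does not spell out, such as nutritional intake, but it does not mention CTCAE either. Items with a planned baseline CTCAE grade: 0 of 10.

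**Step 2. What else is measured at baseline for each item?**

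| Item | Partial baseline proxy | Where |
|---|---|---|
| Dry mouth | PRO-CTCAE severity | Section 28 |
| Dysgeusia | PRO-CTCAE taste item | Section 28 |
| Anorexia | PRO-CTCAE appetite items | Section 28 |
| Generalized weakness | PRO-CTCAE fatigue items; KPS | Sections 28, 26 |
| Weight loss | Weight, BMI, 3-month loss | Section 7.1 |
| Sore throat | OMWQ question 2 (mouth and throat soreness) | Section 28 |
| Dysphagia | Nutritional intake status; OMWQ swallowing (may be skipped) | Sections 7.1, 28 |
| Voice alteration | OMWQ talking (loose; may be skipped) | Section 28 |
| Skin reaction | None structured | |
| Neck edema | None structured | |

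Count with a proxy: 4 (PRO-CTCAE) + 1 (weight) + 1 (soreness) + 2 (swallowing or intake, talking) = 8. Without: 10 − 8 = 2. For these two, only the general examination and the ungraded medical history remain, and the history may date from up to 90 days before registration.

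The OMWQ swallowing and talking items may be left blank by a patient who scores soreness 0, so painless swallowing or voice problems after surgery can go unrecorded there. Weight is the strongest proxy, because it is measured at baseline and at every visit and its change can be computed directly. The questionnaire scores cannot be subtracted from a clinician's CTCAE grade.

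**Step 3. How much do the onset date and attribution recover?** They can mark a symptom as older than RT. They do not give its grade before RT, so they separate old from new better than stable from worsened. They are also completed after exposure, and so rest partly on recall and judgment.

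**Step 4. Can randomization be relied on to balance pre-existing symptoms?** One patient is 1/10 = 10 percentage points with 10 per arm, or 1/12 = 8.3 with 12 per arm. The documents give no prevalence, so p is an assumption. With X₁ and X₂ independent Binomial(n, p), the probability that the arms differ by three or more affected patients is P(|X₁ − X₂| ≥ 3), the sum of P(X₁ = a)·P(X₂ = b) over all |a − b| ≥ 3:

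| Assumed p | n = 10 per arm | n = 12 per arm |
|---|---|---|
| 10% | 6.0% | 8.4% |
| 20% | 15.7% | 19.7% |
| 30% | 22.0% | 26.3% |
| 50% | 26.3% | 30.7% |

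Three patients are 30 percentage points with 10 per arm and 25 with 12. These are chances for a single item. The ten items are likely to be correlated, so they are not combined.

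**The case against.** The strongest reply is that little of consequence hangs on this. Clinician-graded CTCAE toxicity is not among the primary, secondary or exploratory endpoints, and Section 16 plans no test of it between arms. WHO mucositis, the OMWQ and PRO-CTCAE, which are formal endpoints, all have baselines. Allocation is randomized and double-blind, so pre-existing symptoms add noise and do not favour either arm systematically. Suspected rinse effects also have their own diary and observation form. All of this stands, and it limits the point to safety reporting.

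The reply is also right against three stronger readings that a reader might infer.

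- *That pre-existing symptoms cannot be separated from on-study events at all.* Section 11.5 records onset dates and allows a disease-related cause, and baseline proxies exist for most items. Separation is partial, not impossible.
- *That dysphagia present before RT will be counted as a new event.* No section says so. Section 17.1 has no counting rule either way.
- *That dysphagia and voice alteration have no baseline measure, as skin reaction and neck edema do not.* Nutritional intake and the OMWQ give partial information on the first two, so only two items lack a structured measure.

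One could also propose the week 1 grade as a stand-in baseline. The plan does not do so, and that grade would already contain any early effect of the rinse.

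**Conclusion.** The point holds as a modest gap in safety reporting. If the plan is followed exactly, none of the ten items has a CTCAE grade before exposure, so change in grade from before the first rinse cannot be computed. Symptoms already present can be only partly separated, through dates, attribution and proxies on other scales. Those proxies cover eight of the ten items.

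The chance-imbalance figures of 6% to 26% (10 per arm) and 8% to 31% (12 per arm) depend on the assumed 10% to 50% prevalence. They show that balance cannot be taken for granted at this size; they are not evidence that harm will be misjudged. Neither the primary endpoint nor any other formal endpoint is affected.

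**What to change.** Mark the ten-item CTCAE grading in the baseline column of Section 26, to be done before the first rinse at the physical examination already scheduled there, and add it to the baseline list in Section 7.1. In Section 17.1, state that the safety analysis will report by arm the events that are new or worsened from that baseline grade, alongside all recorded events. Keeping both tabulations avoids resting the safety account on one counting convention.

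The cost is a few minutes per patient and one CRF page, with no new visit or procedure. The change needs to be in place before a patient starts rinsing, because the missing grade cannot be collected prospectively afterwards.
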